## **Study protocol**

**Participants:** We aim to recruit a total of 120 participants (60 for the intervention and 60 as a control group).

Inclusion criteria include any gender, age between 40 and 89 years old, illiteracy (TOFHLA score <53) and availability to participate in the study for at least 12 months.

Exclusion criteria will be: A) Presence of remarkable cognitive complaints and/or decompensated psychiatric illness (depression and anxiety) and/or current substance abuse such as alcohol and illicit drugs use. B) Objective cognitive impairment: 2 standard deviations or less for age and education on the Mini-Mental State Evaluation (MMSE) and/or 6 or less points on the delayed recall task from the Brief Cognitive Battery. C) History of previously diagnosed dyslexia D) Formal MRI contraindications including metal or claustrophobia. E) Severe structural lesions detected by MRI.

Informed consent will be written in accessible language and collected using the approach “teach-to-goal developed for vulnerable populations.

First, we will do pair matching with the 120 participants dividing them into two clusters paired for age, sex and baseline non-verbal intelligence and literacy level (by TOFLHA). Next, within each pair, one cluster is randomized to receive the intervention (n=60), and the other cluster receives the placebo (n=60). Based on our pilot project and historical data, we calculate an attrition rate of 20%. Thus, the final sample is expected to have 96 individuals. We will reassess the participants’ cognition and neuroimaging after 6 months.

**Literacy and cognitive reserve assessment:** Reading comprehension and numeracy skills will be evaluated using the Test of Functional Health Literacy in Adults (TOFHLA) that has been validated for Brazilian Portuguese. A score of or lower 53 defines illiteracy. Global cognitive reserve will be assessed with a structured questionnaire available in Portuguese, that includes years of education, leisure activities and occupational attainment. Sociodemographic features, the level of physical exercise, smoking, and alcohol habits, as well as the presence of psychiatric illness, will be addressed with specific questionnaires.

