**Literacy training (intervention):** The basic-literacy training will be given for 6 months. At baseline, participants will be randomized into four classes of 30. Co-I [name], who is an expert in adult education, will oversee the classes and meet the teachers periodically, and each class will count with a certified and experienced lead teacher and teacher aid. Two of the classes of 30 each will be the intervention group. They will receive literacy training based on analytical and phonemic methods for enabling reading and writing. The two other classes of 30 each will be the placebo group. The placebo group will have access to non-literacy classes offered at the adult school, including geography, history, informatics, and sciences, but no literacy-training.

Both the intervention and the placebo groups will attend classes of two hours/day for four days/week. The teachers will record attendance. The follow-up neuroimaging and neuropsychology testing will be done at the 6 months mark. The informed consent will have a session explaining that participants will be randomly assigned to participate in the intervention or placebo group in the first 6 months so that they will be blind to which group they were assigned for at baseline. Based on the literacy-program experience, we expect a dropout rate of 20%. Thus, we expect to have 96 participants concluding the study. Participants who drop out will be monitored by phone calls every three months and will be also reassessed after 6 months, if interested. We will compare the dropout group with the groups that kept the training to see whether there were differences in intelligence or sociodemographic aspects.

**Blood samples:** At the baseline, we will collect blood samples of participants to assess the apolipoprotein E genotype. Upon participant consent, plasma and serum samples will be stored for future analysis of potential peripheral markers associated with cognitive reserve.

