Better Memory with Literacy Acquisition Later in Life

NCT number NCT04473235

Date April, 29th 2024

Statistical analysis plan

Primary outcome:

The episodic memory will be measured using the Free and Cued Selective Reminding test (FCSRT). This test has 3 steps. First, the participant learns 16 figures, 4 each, with the help of semantic cues. After learning the first 16 figures, the participant recalls them three times, with distraction activity between each attempt (counting 20 to 1 backwards). The sum of each immediate free recall is called sum of attempts. It ranges from 0 (the participant does not recall any of the 16 figures in three attempts) to 48 (the participant recalls all the figures). We used this score as a measurement of episodic memory for the primary outcome.

The total raw score on the free recall sum-of-attempts trial from the FCST at the 6 months of follow up will be subtracted by the same score at baseline, in the intervention and control groups. The mean difference in each group will be compared using a paired T-test.

Secondary outcome:

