The intrinsic connectivity between the hippocampus and the prefrontal cortex will be measured using resting state functional MRI. The participants will undergo one MRI scan at baseline and one MRI scan at the 6 months follow up. The BOLD signal (blood oxygen level dependent) will be extracted as follows. First, a reference volume and its skull-stripped version will be generated using a custom methodology of fMRIPrep. Head-motion parameters with respect to the BOLD reference (transformation matrices, and six corresponding rotation and translation parameters) will be estimated. The estimated fieldmap will be then aligned with rigid-registration to the target EPI (echo-planar imaging) reference run. The field coefficients will be mapped on to the reference EPI using the transform. BOLD runs will be slice-time corrected to 1.44s (0.5 of slice acquisition range 0s-2.88s). The BOLD reference will be then co-registered to the T1 reference. Coregistration will be configured with six degrees of freedom. The three global signals will be extracted within the cerebral spinal fluid and the white matter, and the whole-brain masks. Additionally, a set of physiological regressors will be extracted to allow for component-based noise correction. Principal components will be estimated after high-pass filtering the preprocessed BOLD time-series. The confound time series derived from head motion estimates and global signals will be expanded with the inclusion of temporal derivatives and quadratic terms for each. The BOLD time-series will be resampled into standard space, generating a preprocessed BOLD run in a standard space. Age will be included as a covariate in this analysis.

A seed will be placed in each hippocampus (right and left) and the intrinsic functional connectivity, meaning the BOLD activity between each hippocampus and the prefrontal cortex will be calculated at baseline and at the 6 months of follow up. The intrinsic functional connectivity at 6 months will be subtracted from the baseline. The mean difference in each group will be compared using a paired T-test.

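### Each arm is taught in two classes but the SAP's paired t-test ignores class, so it is anti-conservative if change scores are positively correlated within a class

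*Protocol*

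**What the plan says.** **Teaching.** Under Literacy training (intervention), the Protocol states "At baseline, participants will be randomized into four classes of 30" and "Two of the classes of 30 each will be the intervention group"; the other two classes are the placebo group. It adds that "each class will count with a certified and experienced lead teacher and teacher aid". One expert in adult education "will oversee the classes and meet the teachers periodically". Classes run eight hours a week for 6 months, and "The teachers will record attendance".

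**Matching.** Under Participants, the Protocol says "First, we will do pair matching with the 120 participants dividing them into two clusters paired for age, sex", baseline non-verbal intelligence and literacy level, with randomization within each pair. That section speaks of two clusters of 60, while the Literacy training section speaks of four classes of 30. The two descriptions should be reconciled.

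**Analysis.** For the primary outcome (change in free recall), and again for the fMRI outcome, the SAP says "The mean difference in each group will be compared using a paired T-test". It does not say what is paired. For fMRI it adds "Age will be included as a covariate in this analysis". Neither document mentions class, teacher, an ICC, a design effect or a model with a class term.

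**The concern.** People who share a teacher, an aide and classmates for 6 months may change in similar ways. If they do, the mean of each arm carries the average of only two class effects. The t-test estimates its error from the spread of individual differences, which barely registers that component. Matching does not remove it, because the two members of a pair sit in opposite arms and so in different classes. A positive pair correlation makes matters worse: it shrinks the estimated error and leaves the class variance untouched.

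What is at stake is attribution. With two classes per arm, a difference between teachers or classes can be read as an effect of literacy on memory. The SAP has no step showing how much class correlation the result could tolerate.

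**Working it through.** **1. Inputs from the documents.** 120 recruited, 60 per arm, four classes of 30, 20% dropout. The Protocol's completer figure reproduces: 120 × 0.80 = 96, or 48 per arm and 24 per class if losses are even. No alpha, SD, effect size, power or ICC is given, so there is no power calculation to reproduce.

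**2. Assumptions (none in the documents).** Two-sided 5% test; matched pairs across arms; pair members drop out independently, so 60 × 0.8 × 0.8 = 38.4, about 38 complete pairs; SD of change 1; independent class effects with variance ICC; pair correlation r of 0 or 0.3 on the individual residual; no treatment effect.

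**3. Formulas, both arms clustered, equal classes.**
- True variance of the mean pair difference: V = 2(1−ICC)(1−r)/38 + ICC
- Variance the planned test expects: P = [2(1−ICC)(1−r) + ICC × 38/37]/38
- Approximate type I error: 2 × Pr(t on 37 df > 2.026/√(V/P))

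At ICC 0.05 and r = 0: V = 1.9/38 + 0.05 = 0.1000 and P = (1.9 + 0.0514)/38 = 0.0514. The ratio is 1.947, the effective critical value is 2.026/1.395 = 1.452, and the error is about 15.5%.

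If only the literacy arm clusters, the class terms halve: V = 0.05 + 0.025 = 0.075, P = (1.9 + 0.0257)/38 = 0.0507, ratio 1.480, error about 10.4%.

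**4. Simulation.** 60 pairs, 30 per class, independent 20% dropout; 20,000 trials with both arms clustered and 15,000 with one. The first four result columns are type I error in %. The last is the 95% half-width in SD that the test reports against the one needed (both arms, r = 0).

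| ICC | Both arms, r=0 | Both arms, r=0.3 | Literacy only, r=0 | Literacy only, r=0.3 | Half-width reported / needed |
|---|---|---|---|---|---|
| 0 | 5.1 | 4.9 | – | – | 0.465 / 0.465 |
| 0.01 | 7.1 | 8.0 | 6.3 | 6.5 | 0.464 / 0.505 |
| 0.02 | 9.4 | 11.2 | 7.0 | 8.2 | 0.463 / 0.542 |
| 0.05 | 15.8 | 19.7 | 10.2 | 12.9 | 0.459 / 0.641 |
| 0.10 | 25.0 | 30.1 | 15.9 | 20.0 | 0.453 / 0.778 |

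Repeat runs with slightly different set-ups moved some figures by about a point (to 31% and 14% at the upper ends), so the ranges quoted in the conclusion are a little wider than the table. The choice of 38 pairs is the mild case: with 48 complete pairs, the both-arms error at ICC 0.05 is about 18% (r = 0) to 23% (r = 0.3).

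**5. Loss of significance.** Set V/P = (t_obs/2.026)², with t_obs = 2.257, 2.715 and 3.574 for unadjusted p = 0.03, 0.01 and 0.001. With both arms clustered, p passes 0.05 at ICC 0.013, 0.042 and 0.108 (r = 0), or 0.009, 0.030 and 0.078 (r = 0.3).

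**6. Other readings of the test.**
- Baseline versus follow-up within one arm, two classes of 24: type I error 7.6%, 10.5%, 18.1% and 28.7% at ICC 0.01, 0.02, 0.05 and 0.10.
- Unpaired test between arms, both clustered, r = 0: 7.7%, 10.7%, 18.4% and 28.9%. If a pair correlation of 0.3 is ignored, it is 2.4% at ICC 0 and 5.1% at ICC 0.01, so the matching offsets a very small ICC.

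**7. Does the correction work?** With the true ICC inserted, the both-arms formula given in the fix holds type I error at 4.4–5.1% when both arms cluster. When only the literacy arm clusters it over-corrects, to about 2% and 1% at ICC 0.05 and 0.10. Counting only the literacy classes restores about 4–6%. Hence two scenarios are needed.

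**8. Class-level t-test.** Four class means, 2 df, critical t 4.303, SE = √(ICC + (1−ICC)/24). Power for an assumed 0.5 SD effect is about 29%, 25%, 22%, 17% and 13% at ICC 0, 0.01, 0.02, 0.05 and 0.10.

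**The case against.** The best defence is that nothing in the documents shows the ICC to be above zero. Participants are randomized into classes, so classes should not differ systematically at baseline and any correlation must arise during teaching. The primary outcome is recall of 16 figures, not course content. A single expert oversees all classes, which may narrow differences between them. For fMRI the documents neither suggest nor exclude a class effect. All of this stands as a limit on size. None of it enters the analysis, and a zero ICC remains an assumption that the SAP does not state.

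The placebo arm may also cluster less. The Protocol offers it several school subjects and does not say that each group of 30 stays together with one teacher across them. That stands too, and is why the literacy-only figures are given equal place.

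It is also fair to say that a class-level analysis has little power and that two classes per arm is a design limit no SAP wording removes. The fix therefore keeps the t-test.

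Three stronger readings are tempting:
- A reader might infer that the trial's false-positive rate is 25–31%. That needs an ICC of 0.10 in both arms, which the documents do not support.
- A reader might infer from the word clusters under Participants that whole groups of 60 were randomized. The Literacy training section says that participants are randomized into classes, so the documents do not establish this.
- A reader might infer that the issue disappears if the pairing is baseline versus follow-up. It does not: that test is inflated as well, and it makes no comparison between arms.

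**Conclusion.** The concern holds in conditional form. Under the matched-pair reading, the planned test is anti-conservative for any positive within-class ICC of change. It is correct at ICC 0 and not anti-conservative if the ICC is negative. The direction is settled; the size is not, because the documents supply no ICC.

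Under the stated assumptions, type I error at ICC 0.02, 0.05 and 0.10 is about 9–11%, 15–20% and 25–31% with both arms clustered, and about 7–8%, 10–14% and 16–20% with the literacy arm only. If the pairing is within arm, the error is about 8–29% over ICC 0.01 to 0.10. Small ICCs matter mainly for borderline results: an unadjusted p of 0.03 is lost at an ICC near 0.01 when both arms cluster. This should be fixed, but it does not show that the trial's result would be wrong.

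**What to change.** 1. State that the primary test compares change between arms, and whether it is on matched pairs.
2. Record class and lead teacher for each participant, and report the four class means with the result.
3. Keep the t-test and add a sensitivity analysis giving SE, p-value and 95% CI at assumed ICCs of 0, 0.01, 0.02, 0.05 and 0.10, plus the smallest ICC at which significance is lost, with no pass/fail value. For matched pairs, on n−1 df, use two labelled scenarios:
   - Both arms clustered, equal ICC: SE² = s_d²/n + [ICC/(1−ICC)] × s_w² × [S − (2−S)/(n−1)].
   - Literacy arm only: replace the last bracket by [S_L − (1−S_L)/(n−1)].

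   Here n is the number of analysed pairs, s_d² the variance of the pair differences, and s_w² the pooled within-class variance of individual change. S is the sum over all four classes of (analysed pairs in class/n)², which is 1 if classes are equal. S_L is the same sum over the two literacy classes.
4. Report the class-level t-test (2 df) as supportive only, noting its low power.
5. State that with two classes per arm the literacy effect cannot be fully separated from class or teacher effects.
6. For fMRI, apply the same sensitivity analysis to age-adjusted change (residuals from the age-adjusted model, with df reduced for the covariate), noting that the documents are silent on a class effect there.

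The cost is SAP wording, two variables and a short table, with no change to recruitment or teaching. The price is a wider interval and a more qualified conclusion. Two things are unknown: whether class and teacher were recorded, and whether outcomes are already known (the SAP is dated April 2024 and partly written in the past tense). If class data exist or outcomes are known when this is added, label it post hoc rather than pre-specified.

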Better Memory with Literacy Acquisition Later in Life

NCT number NCT04473235

Date April, 29th 2024

Statistical analysis plan

Primary outcome:

The episodic memory will be measured using the Free and Cued Selective Reminding test (FCSRT). This test has 3 steps. First, the participant learns 16 figures, 4 each, with the help of semantic cues. After learning the first 16 figures, the participant recalls them three times, with distraction activity between each attempt (counting 20 to 1 backwards). The sum of each immediate free recall is called sum of attempts. It ranges from 0 (the participant does not recall any of the 16 figures in three attempts) to 48 (the participant recalls all the figures). We used this score as a measurement of episodic memory for the primary outcome.

The total raw score on the free recall sum-of-attempts trial from the FCST at the 6 months of follow up will be subtracted by the same score at baseline, in the intervention and control groups. The mean difference in each group will be compared using a paired T-test.

Secondary outcome:

The intrinsic connectivity between the hippocampus and the prefrontal cortex will be measured using resting state functional MRI. The participants will undergo one MRI scan at baseline and one MRI scan at the 6 months follow up. The BOLD signal (blood oxygen level dependent) will be extracted as follows. First, a reference volume and its skull-stripped version will be generated using a custom methodology of fMRIPrep. Head-motion parameters with respect to the BOLD reference (transformation matrices, and six corresponding rotation and translation parameters) will be estimated. The estimated fieldmap will be then aligned with rigid-registration to the target EPI (echo-planar imaging) reference run. The field coefficients will be mapped on to the reference EPI using the transform. BOLD runs will be slice-time corrected to 1.44s (0.5 of slice acquisition range 0s-2.88s). The BOLD reference will be then co-registered to the T1 reference. Coregistration will be configured with six degrees of freedom. The three global signals will be extracted within the cerebral spinal fluid and the white matter, and the whole-brain masks. Additionally, a set of physiological regressors will be extracted to allow for component-based noise correction. Principal components will be estimated after high-pass filtering the preprocessed BOLD time-series. The confound time series derived from head motion estimates and global signals will be expanded with the inclusion of temporal derivatives and quadratic terms for each. The BOLD time-series will be resampled into standard space, generating a preprocessed BOLD run in a standard space. Age will be included as a covariate in this analysis.

A seed will be placed in each hippocampus (right and left) and the intrinsic functional connectivity, meaning the BOLD activity between each hippocampus and the prefrontal cortex will be calculated at baseline and at the 6 months of follow up. The intrinsic functional connectivity at 6 months will be subtracted from the baseline. The mean difference in each group will be compared using a paired T-test.

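### The primary analysis compares raw FCSRT change with no baseline covariate; adjusting for the baseline score already collected would probably, not certainly, be more precise

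*SAP*

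**What the plan says.** The SAP, under Primary outcome, takes the FCSRT free-recall sum over three attempts (range 0 to 48). The 6-month score "will be subtracted by the same score at baseline, in the intervention and control groups". It continues: "The mean difference in each group will be compared using a paired T-test". No model and no covariate is named for this outcome.

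The only covariate in the SAP belongs to the connectivity analysis under Secondary outcome: "Age will be included as a covariate in this analysis".

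The protocol, under Participants, describes taking the 120 participants and "dividing them into two clusters paired for age, sex and baseline non-verbal intelligence and literacy level". Baseline FCSRT is not among these factors, although the test is part of the cognitive evaluation and the change score needs it at baseline. After attrition, "the final sample is expected to have 96 individuals".

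**The concern.** A change score is the 6-month score minus exactly once the baseline score. That is the best weight only if the slope of 6-month score on baseline score is 1. For a memory test repeated after six months the slope may well be lower, because part of the baseline score is measurement noise. Subtracting all of it then carries that noise into the outcome. A linear model that estimates the slope avoids this.

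Baseline FCSRT is neither balanced by the matching nor given an estimated slope, so chance differences between arms at baseline are handled only by the fixed weight of 1. With about 96 completers, precision on the primary outcome is limited, and some of it may be given up although the baseline score is in hand. What is at stake is the width of the confidence interval and the power, not the validity of the estimate.

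**Working it through.** **Inputs from the documents.** 120 recruited, 60 per arm, 20% attrition: 120 × (1 − 0.20) = 96. This reproduces the protocol's figure and gives 48 per arm if dropout is equal. Each arm has two classes.

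**Inputs assumed, because neither document gives them.** Correlation ρ between baseline and 6-month score: 0.4, 0.6, 0.8. Baseline SD 1 and 6-month SD k, with k = 1 unless stated. Class variance and the strength of the matching factors as stated below. The comparator is the between-arm difference in mean change.

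**Step 1: independent participants.**

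- Variance with change = (2/48)(k² + 1 − 2ρk).
- Variance with baseline adjustment = (2/48) k²(1 − ρ²) × f, where f = 1 + 1/(96 − 1 − 3) = 1.0109 is the cost of estimating one slope.

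With k = 1 and f = 1 the ratio is (1 − ρ²)/[2(1 − ρ)] = (1 + ρ)/2:

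| ρ | Ratio, f = 1 | Reduction | Reduction with f = 1.0109 |
|---|---|---|---|
| 0.4 | 0.84/1.20 = 0.70 | 30% | 29.2% |
| 0.6 | 0.64/0.80 = 0.80 | 20% | 19.1% |
| 0.8 | 0.36/0.40 = 0.90 | 10% | 9.0% |

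Simulation (40,000 trials per cell) gave 29.2/19.1/9.1%. The mean error of both estimators was at most 0.002 SD, so neither is biased. Break-even is at ρ = (2 − f)/f = 0.978.

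**Step 2: pair matching.** Suppose 60 pairs are identical on the matching factors, these explain R² of baseline FCSRT and act on follow-up only through it, and 20% drop out at random. On average 60 × 0.8 × 0.8 = 38.4 pairs stay intact, which is 80% of 48. The variance of the change comparison becomes (2/48)[(1 − ρ)²(1 − 0.8R²) + (1 − ρ²)].

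- R² = 0.3: the brackets are 1.1136, 0.7616 and 0.3904, against 0.84, 0.64 and 0.36 after adjustment. Reductions before slope cost are 24.6/16.0/7.8%. Simulation with the slope cost (60,000 trials per cell) gave 24.2/15.5/7.2%.
- R² = 0.5: simulation gave 20.2/12.7/5.8%.

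**Step 3: classes.** With class variance 0.05 (individual outcome variance 1) and two classes per arm, both variances gain 2 × 0.05/2 = 0.05. Without matching or slope cost:

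- ρ = 0.4: 0.1000 against 0.0850, reduction 15.0%.
- ρ = 0.6: 0.0833 against 0.0767, reduction 8.0%.
- ρ = 0.8: 0.0667 against 0.0650, reduction 2.5%.

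**Step 4: both.** Adding 0.05 to the R² = 0.3 variances of Step 2 gives 0.0964 against 0.0850, 0.0817 against 0.0767 and 0.0663 against 0.0650: about 12/6/2%, before slope cost.

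**Step 5: unequal SDs, independent participants, f = 1.0109.** The true slope is ρk.

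- k = 1.25: reductions 15.1/4.9/−1.1%. At ρ = 0.8 the slope is exactly 1, both variances are proportional to 0.5625, and only the slope cost remains.
- k = 0.8: about 46/39/35%.

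**Step 6: adding age, sex, Beta-3 and TOFHLA.** With five covariates f = 1 + 5/(96 − 5 − 3) = 1.0568. If the four extra variables predict nothing beyond baseline and are not balanced, the Step 1 reductions become 26.0/15.5/4.9%, about 3 to 4 points lower. Under exact matching with R² = 0.3 they are 23.4/14.6/6.2%, about 1 point below baseline alone.

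**The case against.** The strongest case against acting is that nothing here is invalid and every driver of the gain is assumed. Across the assumptions above, baseline adjustment ranges from a gain of about 46% to a loss of about 1%, and the documents do not say where this trial lies. The figures for independent participants ignore both matching and classes. With both present, an assumed 5% class variance and R² = 0.3, the gain at ρ = 0.8 is only about 2%. The comparison also presumes a between-arm contrast, which the SAP's reference to a paired t-test does not clearly specify.

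Most of this stands, and it limits the size that can be claimed. It does not remove the point, because the risk is lopsided: the possible loss is about 1% of variance, the possible gain is several times that over most of the assumed range, and the data are already collected. The meaning of the paired test and the handling of classes are separate issues that must be settled in their own right.

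A reader might infer more than the documents support:

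- **That the change score is biased.** It is not, under randomisation. Informative dropout could distort either analysis and does not favour one here.
- **That the matching variables should be added to gain precision.** In the scenarios computed above, which credit them with no prediction beyond baseline FCSRT, they reduce the gain. Any further predictive value would have to be assumed.
- **That connectivity would gain in the same way.** No figure supports that.

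**Conclusion.** The point holds as a matter of efficiency. The primary analysis fixes the baseline slope at 1 when the slope could be estimated from data in hand. Adjusting for baseline FCSRT alone is likely to lower the variance of the arm difference. The 29/19/9% for independent participants is best read as the upper end under equal SDs. The matched and class-taught design points to smaller gains, down to about 12/6/2% with both features at the values assumed. The gain disappears when the true slope is near 1.

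All of these sizes rest on assumed correlations, SDs, class variance and matching strength, with 48 completers per arm. The finding is a low-cost improvement. It does not show that the planned estimate is wrong or misleading.

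**What to change.** Once the SAP states the primary comparison as between-arm:

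- Analyse the 6-month FCSRT free-recall sum in a linear model on arm and baseline FCSRT.
- Report the adjusted arm difference with its 95% confidence interval.
- Keep mean change per arm as a descriptive result.
- Fix the model and covariate list in the SAP before the outcome data are analysed.

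Adding age, sex, Beta-3 and TOFHLA is optional. The reason to do so would be to reflect the matched design, not the efficiency figures above. A class term is a separate decision with its own substantial loss of degrees of freedom, and is not part of this proposal.

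The cost is one short SAP paragraph and no new data. Baseline alone uses one residual degree of freedom (94 to 93). Even all five covariates leave 89, with a critical value of 1.987 against 1.986.

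### The primary change-score test uses only participants with both scores and adjusts for nothing, so arm-specific dropout could bias it by roughly 0.1 SD; baseline adjustment and one sensitivity analysis would be a cheap improvement

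*SAP*

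**What the plan says.** Under Participants, the protocol states: "We aim to recruit a total of 120 participants (60 for the intervention and 60 as a control group"). It gives 20% attrition both there and under Literacy training. The latter section concludes: "Thus, we expect to have 96 participants concluding the study".

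For those who leave, the Literacy training section offers follow-up: "Participants who drop out will be monitored by phone calls every three months and will be also reassessed after 6 months, if interested". It also plans a descriptive check: "We will compare the dropout group with the groups that kept the training to see whether there were differences in intelligence or sociodemographic aspects". That check is not stated to be by arm, does not list baseline memory, and has no stated consequence for the primary analysis.

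The SAP's primary outcome section defines the outcome as the free-recall sum of attempts (0 to 48) at 6 months, which "will be subtracted by the same score at baseline, in the intervention and control groups". The group mean differences are then compared by a paired t-test. No covariate, analysis population, missing-data method or sensitivity analysis is given. Age is named as a covariate only in the section on hippocampal connectivity.

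The Participants section matches on age, sex, non-verbal intelligence and TOFHLA literacy. Baseline recall is not a matching variable.

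**The concern.** A change score needs both visits, so with no missing-data method the analysis is complete-case by default, although the SAP never uses that term. Such an analysis estimates the randomised contrast without bias only if those who are missing do not distort mean change differently in the two arms.

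The arms attend different classes: literacy training in one, and geography, history, informatics and sciences in the other. Reasons for leaving could therefore differ by arm. If they do, and if they relate to baseline recall or to how memory is changing, part of the observed difference is selection.

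The trial collects baseline recall and the other baseline variables that could remove the part they explain, but the planned test uses none of them as covariates. The dropout comparison might reveal a problem, yet the plan gives no way to act on it.

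**Working it through.** **1. The plan's own figure.** 120 × (1 − 0.20) = 96, which reproduces. The expected loss is 120 − 96 = 24, or 12 per arm if equal (48 remaining in each). Because reassessment is offered, 24 is a ceiling at the stated rate.

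**2. If the test is on matched pairs.** Losing either member loses the pair. With independent dropout, 60 × 0.8² = 38.4, or about 38 pairs and 77 people rather than 96.

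**3. A general bound.** Bias in an arm's mean change = missing fraction × (completer mean change − dropout mean change). With 20% missing, a gap of 0.5 SD gives 0.20 × 0.5 = 0.10 SD, and a gap of 1 SD gives 0.20 SD.

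**4. Dropout driven by baseline recall.** The documents give no SD, correlation or dropout pattern, so the following are assumptions: score SD 1 at both visits, baseline-to-6-month correlation ρ of 0.5 to 0.7, 20% lost per arm, logistic dropout with odds ratio 2 per SD, no true effect.
- Mean baseline recall among stayers is then shifted by 0.129 SD (numerical integration).
- Change regresses on baseline with slope ρ − 1, that is −0.5 to −0.3.
- One arm only: 0.129 × 0.3 = 0.04 to 0.129 × 0.5 = 0.06 SD.
- Opposite directions: 2 × 0.129 × 0.3 = 0.08 to 2 × 0.129 × 0.5 = 0.13 SD.
- Same selection in both arms: zero.

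Simulation of the opposite-direction case gave about 0.11 SD unpaired and 0.09 SD on matched pairs. Adjusting for baseline recall brought this to about zero, with a smaller spread of the estimate (0.167 against 0.18 to 0.20 SD).

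With stronger selection (logistic slope 1 per SD, odds ratio e¹ ≈ 2.7), the unadjusted bias was 0.05 to 0.09 SD for one arm and 0.10 to 0.17 SD for opposite directions. It was again about zero after adjustment. The sign is against literacy training if its low recallers leave.

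**5. Dropout driven by the change itself** (same slope of 1). Unadjusted bias was 0.11 to 0.17 SD for one arm and 0.22 to 0.34 SD for opposite directions. Baseline adjustment left 0.10 to 0.13 and 0.19 to 0.26 SD. Here the sign favours literacy training if its poor improvers leave. Adjustment does not solve this case.

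**6. Dropout driven by matched ability.** For an unpaired test with 48 per arm, SE = √(2/48) = 0.204 SD of change. Assume an ability–change correlation of 0.3 to 0.4.
- Odds ratio 2, one arm: 0.129 × 0.3 = 0.04 to 0.129 × 0.4 = 0.05 SD; two-sided error 5.4% to 5.7%.
- Odds ratio 2, opposite directions, correlation 0.4: 2 × 0.129 × 0.4 = 0.10 SD, or 0.50 SE; error about 8.0%.
- Odds ratio 3 (stayer shift 0.186), opposite directions, correlation 0.4: 2 × 0.186 × 0.4 = 0.15 SD; error about 11%.
- Odds ratio 2, correlation 0.1: 0.01 to 0.03 SD; error 5.0% to 5.2%.

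The odds-ratio-3 case run as a matched-pair test gave bias 0.00 SD and error 4.5% with perfect matching on ability. With within-pair ability correlation 0.8 it gave 0.04 SD and 5.0%, and with 0.5 it gave 0.08 SD and 6.2%.

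**The case against.** The strongest reply is that the SAP says paired and the protocol matches on ability. A test on intact pairs keeps the arms matched, so dropout driven only by the matching variables is largely neutralised. That stands, with two limits. Baseline recall is not matched, so selection on it, or on the change itself, still biases a paired test. The paired reading also costs about 22 of 60 pairs. The wording is ambiguous as well: if it means before against after within each arm, there is no between-arm test at all.

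A second reply is that the bias is hypothetical. This also stands in part. Nothing in the documents shows that dropout will differ by arm, still less in opposite directions, and the correlations used above are assumptions. Voluntary reassessment should reduce the number missing.

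A reader might infer that the primary result will be biased, or that the false-positive rate will reach 8% to 11%. The documents do not support either. Those error rates need an unpaired test together with opposite-direction selection and a fairly strong link between ability and change.

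A third reply is that imputation cannot repair dropout that depends on unseen scores. That is correct, and it is why a shift-based sensitivity analysis is needed as well as adjustment.

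**Conclusion.** The point holds as a conditional weakness. The plan expects up to 24 of 120 to leave, fixes a primary test that discards anyone without both scores, and ignores baseline data that would protect against one plausible kind of selective loss. The likely scale is about 0.1 SD under moderate opposite-direction selection on baseline recall, about half that with selection in one arm, and nil with equal selection. Dropout tied to the change itself could do more, and adjustment would remove little of that. Size and direction cannot be known from the documents, and all SD figures rest on the stated assumptions. It is a cheap improvement to make before results are known, and does not show that the planned analysis is invalid.

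**What to change.** In the SAP's primary outcome section, replace the unadjusted change-score test with a between-arm model of the 6-month FCSRT score. Adjust for baseline FCSRT and the matching variables (age, sex, Beta-3, TOFHLA), with whatever pair or class terms are adopted. Include everyone with a 6-month score, and count reassessed dropouts in their randomised arm.

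Add one sensitivity analysis: multiple imputation of missing 6-month scores, separately by arm, from these baseline variables and education. Then shift the imputed literacy-arm scores progressively downward until the conclusion changes. The imputation model must be compatible with any pair or class terms in the analysis model. Attendance should not be a required imputation variable: it is measured after randomisation, and people who leave stop attending, so using it forces extrapolation.

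The cost is SAP wording and a little more programming, with no new data or participants. The downside is reliance on a stated model, which the tipping-point analysis partly tests.
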